8.4.2.3 Visit 7/Early Termination (Week 12)

- Prior to any other test or evaluations, administer PRO measures including: HIT-6, PGIC, PGI-S, WPAI:MIGRAINE, PSSM, MIDAS, MSQ v2.1, PROMIS-PI, and PHQ-9.
- Perform physical examination.
- Review eDiary data (participants must bring eDiary to visits).
- Collect eDiary from participant, if the participant completed the treatment period (eDiary collection will occur at Visit 8 for participants who discontinue study intervention early [see Section 8.8.1]).
- Perform urine pregnancy test for women of childbearing potential.
- Collect vital sign measurements including: weight, sitting and standing pulse rate, respiratory rate, sitting and standing BP, and body temperature.
- Collect start date (first day) of last menstrual cycle for women having menstrual cycles.
- Assess C-SSRS (the “Since Last Visit” assessment of the C-SSRS will be completed).
- Perform and transmit ECG.
- Update concomitant medications and concurrent procedures (including all prior headache medications).
- Collect previous visit study intervention, review participant compliance, and perform accountability.

- Review and assess AEs.
- Access IWRS and enter accountability.
- Collect PK sample (for those participants who consented). The PK sample should be collected 1 to 10 hours post the morning dose.
- Collect blood and urine samples for chemistry, hematology, INR, and urinalysis.

8.4.3 Follow-up Period (4 Weeks)

8.4.3.1 Visit 8/End of Study (Week 16)

- Prior to any other test or evaluations, administer PRO measures including: EQ-5D-5L, HIT-6, and MSQ v2.1.
- Collect eDiary from participant, if the participant discontinued study intervention early [see Section 8.8.1]).
- Perform physical examination.
- Assess C-SSRS (the “Since Last Visit” assessment of the C-SSRS will be completed).
- Collect vital sign measurements including: weight, sitting and standing pulse rate, respiratory rate, sitting and standing BP, and body temperature.
- Collect start date (first day) of last menstrual cycle for women having menstrual cycles.
- Perform urine pregnancy test for women of childbearing potential.
- Collect blood and urine samples for chemistry, hematology, INR, and urinalysis.
- Update concomitant medications and concurrent procedures (including all prior headache medications).
- Review and assess AEs.
- Access IWRS to enter study visit.

8.5 Instructions for the Participants

Section 4.4.4 provides diet and activity instructions for participants enrolled in the study.

Participants will be provided with instructions on daily completion of the eDiary. A practice session with a hypothetical scenario should be administered to ensure the participant’s comprehension of the questions and the information to be entered. In addition, prohibited

medications should be reviewed with the participants. Participants will be instructed to bring their eDiary to each clinic visit and return their study intervention (used and unused blister packs).

Participants should be instructed to take study intervention BID at approximately the same times each day (approximately 12 hours between doses). For dosing on Day 1 (Visit 2), the first dose is to be taken at the study site, and participants should be advised to take the second dose depending on the time of the site visit and the participant's usual routine. Study intervention may be taken with or without food. Water is allowed as desired.

Participants should use appropriate contraceptive measures for the duration of their participation in the study (see Section 4.4.3).

8.6 Unscheduled Visits

Additional examinations and laboratory assessments may be performed as necessary to ensure the safety and well-being of the participants during the study period. Unscheduled visit eCRFs should be completed for each unscheduled visit.

8.7 Compliance with Protocol

All assessments will be conducted at the appropriate visits as outlined in Table 1, and the timing of the visits should occur as close as possible to the day specified. At each visit, the participant will be asked if the participant changed the dose/regimen of any existing concomitant medications or initiated the use of any new concomitant medications since the last visit to ensure compliance with the protocol.

Study intervention compliance during any period will be closely monitored by counting the number of tablets dispensed and returned. Every effort will be made to collect all unused study intervention.

8.8 Early Discontinuation of Participants

A premature discontinuation will occur when a participant who signed the ICF and has been randomized ceases participation in the study, regardless of circumstances, before completion of the study. Participants can be prematurely discontinued from the study for one of the following reasons:

- AE
- Lack of efficacy
- Lost to follow-up
- Non-compliance with study intervention
- Other (specify reason)
- Pregnancy
- Protocol deviation
- Site terminated by sponsor
- Study terminated by sponsor
- Withdrawal by participant

[figure not shown]
Participants may voluntarily withdraw from the study at any time. Notification of early participant discontinuation from the study and the reason for discontinuation will be made to the sponsor and will be clearly documented on the appropriate eCRF. All randomized participants who prematurely discontinue from the study, regardless of cause, should be seen for final study assessments. The final assessments will be defined as completion of the evaluations scheduled for Visit 7/ET and Visit 8 (follow-up), 4 weeks post the last dose of study intervention.

8.8.1 Participants Who Discontinue Study Intervention Early

All participants who discontinue study intervention early (defined as prior to Week 12 [Visit7]) for reasons other than withdrawal of consent or lost to follow-up should remain in the study for the purpose of collecting efficacy data to support the estimand framework for EMA. These participants should return to the clinic for ET procedures (Visit 7) and the Follow-up Visit (Visit 8) per the Schedule of Visits and Procedures (Table 1). If Visit 8 occurs on or after Week 12 (relative to randomization), no Final Study Visit is required (Figure 2, Scenario A). If Visit 8 occurs before Week 12 (relative to randomization) participants should return to the clinic

for an additional Final Study Visit to be scheduled 12 weeks after randomization (Day 84 +7 days, Figure 2, Scenario B).

Figure 2 Study Diagram for Estimand Framework

Note the following changes to the Schedule of Visits and Procedures for participants who discontinue study intervention early:

- Participants should continue to complete eDiary assessments daily until Visit 8 or the Final Study Visit (if required) to allow for the collection of at least 12 weeks of efficacy data.
- eDiaries should be collected at the participant's last study visit (Visit 8 or at the Final Study Visit [if required]).
- PROs should be administered on the eTablet as follows:
 - Scenario A - Visit 8 is the final study visit:
 - Visit 7/ET PROs should be collected as per the Schedule of Visits and Procedures
 - Visit 8 PROs will include those expected to be collected per the Schedule of Visits and Procedures and the HIT-6
 - Scenario B – Visit 8 is not the final study visit:
 - Visit 7/ET PROs should be collected as per the Schedule of Visits and Procedures
 - Visit 8 PROs should be collected as per the Schedule of Visits and Procedures
 - Final Study Visit PROs will include MSQ v2.1 and HIT-6
- If a Final Study Visit is required, concomitant medications/concurrent procedures should also be assessed.

8.9 Withdrawal Criteria

Women who become pregnant (Section 9.4) and participants who meet study intervention discontinuation criteria related to abnormal liver function tests (Section 9.5), and advised not to be rechallenged, will be withdrawn from the study and should refrain from taking study intervention. The participant should return to the clinic for ET procedures (Visit 7) and the Follow-up Visit (Visit 8). Participants who reply with “yes” to questions 4 or 5 in the suicidal ideation section or “yes” to any question in the suicidal behavior section of the C-SSRS at Visits 3 through 6 must be withdrawn from the study and should receive appropriate follow-up as in routine clinical practice, including the ET Visit (Visit 7) and the Follow-up Visit (Visit 8).

A participant with a condition and/or a situation that, in the investigator's opinion, may put the participant at significant risk, may confound the study results, or may interfere significantly with the participant's participation in the study may be withdrawn from treatment.

8.10 Study Termination

The study may be stopped at his/her study site at any time by the site investigator. The sponsor may stop the study (and/or the study site) for any reason with appropriate notification.

9. Adverse Events

AEs occurring during the study will be recorded on an AE CRF. If AEs occur, the first concern will be the safety of the study participants.

9.1 Definitions

9.1.1 Adverse Event

An AE is any untoward medical occurrence in a patient or clinical study participant associated with the use of study intervention, whether or not considered related to the study intervention. An AE can therefore be any unfavorable and unintended sign (including an abnormal laboratory finding), symptom, or disease (new or exacerbated) temporally associated with the use of study intervention. In addition, during the screening period, AEs will be assessed regardless of the administration of a pharmaceutical product.

AEs will be reported by the participant (or, when appropriate, by a caregiver, surrogate, or the participant's legally authorized representative).

The investigator and any qualified designees are responsible for detecting, documenting, and recording events that meet the definition of an AE or SAE and remain responsible for following up AEs that are serious, considered related to the study intervention or study procedures, or that caused the participant to discontinue the study intervention or study (see Section 8.8).

All AEs must be collected once informed consent has been obtained, regardless of whether or not the participant has been administered study intervention, until the Follow-up Visit (Visit 8) or 30 days after the last dose of study intervention if the Follow-up Visit is not done. These will be collected at the timepoints specified in the Schedule of Visits and Procedures (Table 1), and as observed or reported spontaneously by study participants. Investigators are not obligated to actively seek AE information after conclusion of the study participation.

AEs will be assessed, documented, and recorded in the eCRF throughout the study (ie, after informed consent has been obtained). At each visit, the investigator will begin by querying for AEs by asking each participant a general, non-directed question such as “How have you been feeling since the last visit?” Open-ended and non-leading verbal questioning of the participant is the preferred method to inquire about AE occurrences. Care will be taken not to introduce bias when detecting AEs and/or SAEs. All reported AEs will be documented on the appropriate eCRF.

9.1.2 Serious Adverse Event

SAEs must meet both the AE criteria described above and the seriousness criteria listed below:

An SAE is defined as any untoward medical occurrence that, at any dose:
a. Results in death
b. Is life threatening The term life threatening in the definition of serious refers to an event in which the participant was at risk of death at the time of the event. It does not refer to an event, which hypothetically might have caused death, if it were more severe.
c. Requires inpatient hospitalization or prolongation of existing hospitalization In general, hospitalization signifies that the participant has been detained (usually involving at least an overnight stay) at the hospital or emergency ward for observation and/or intervention that would not have been appropriate in the physician’s office or outpatient setting. Complications that occur during hospitalization are AEs. If a complication prolongs hospitalization or fulfills any other serious criteria, the event is serious. When in doubt as to whether hospitalization occurred or was necessary, the AE should be considered serious. Hospitalization for elective intervention of a pre-existing condition that did not worsen from baseline is not considered an AE.

d. Results in persistent disability/incapacity

- The term disability means a substantial disruption of a person's ability to conduct normal life functions.
- This definition is not intended to include experiences of relatively minor medical significance such as uncomplicated headache, nausea, vomiting, diarrhea, influenza, and accidental trauma (eg, sprained ankle) which may interfere with or prevent everyday life functions but do not constitute a substantial disruption.

e. Is a congenital anomaly/birth defect**f. Other situations:**

- Medical or scientific judgment should be exercised in deciding whether SAE reporting is appropriate in other situations such as important medical events that may not be immediately life threatening or result in death or hospitalization but may jeopardize the participant or may require medical or surgical intervention to prevent one of the other outcomes listed in the above definition. These events should usually be considered serious.

Examples of such events include invasive or malignant cancers, intensive intervention in an emergency room or at home for allergic bronchospasm, blood dyscrasias or convulsions that do not result in hospitalization, or development of drug dependency or drug abuse.

The sponsor considers all cancer AEs as SAEs. The sponsor considers any spontaneous abortion as an SAE. Elective abortions can be SAEs or AEs depending on the reason for the elective abortion (eg, fetal death, still birth, congenital anomalies, ectopic pregnancy, which would make the elective abortion an SAE).

Pre-planned surgeries or procedures for pre-existing, known medical conditions for which a participant requires hospitalization is not reportable as an SAE.

Any pre-planned surgery or procedure should be clearly documented in the site source documents by the medically qualified investigator at the time of the participant's entry into the study. If it has not been documented at the time of the participant's entry into the study, then it should be documented as a SAE and reported to the sponsor.

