9.1.3 Intensity

The intensity assessment for a clinical AE must be completed using the following definitions as guidelines:

Assessment of Intensity	
MILD	A type of AE that is usually transient and may require only minimal treatment or therapeutic intervention. The event does not generally interfere with usual activities of daily living.
MODERATE	A type of AE that is usually alleviated with additional specific therapeutic intervention. The event interferes with usual activities of daily living, causing discomfort but poses no significant or permanent risk of harm to the research participant.
SEVERE	A type of AE that interrupts usual activities of daily living, or significantly affects clinical status, or may require intensive therapeutic intervention.

An event is defined as *serious* when it meets at least one of the predefined outcomes as described in the definition of an SAE, NOT when it is rated as severe.

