9.1.5 Follow-up of Adverse Events and Serious Adverse Events

After the initial AE/SAE report, the investigator is required to proactively follow each participant at subsequent visits/contacts. All AEs/SAEs and non-serious AEs of special interest (as defined in Section 6.5.2) will be followed until resolution, stabilization, the event is otherwise explained, or the participant is lost to follow-up (as defined in Section 8.8).

The investigator is obligated to perform or arrange for the conduct of supplemental measurements and/or evaluations as medically indicated or as requested by the sponsor to elucidate the nature and/or causality of the AE or SAE as fully as possible. This may include

additional laboratory tests or investigations, histopathological examinations, or consultation with other health care professionals.

New or updated information will be recorded in the originally completed eCRF.

The investigator will submit any updated SAE data to the sponsor within 24 hours of receipt of the information.

9.1.6 Adverse Reactions, Serious Adverse Reactions, and Suspected Unexpected Serious Adverse Reactions

For the purposes of expedited reporting within the EU, the sponsor will follow the applicable definitions for ARs, SARs, and SUSARs (for example, as outlined in Article 2 [n,o,p] of Directive 2001/20/EC, see below). Also, seriousness criteria for AEs/ARs (as would apply to SARs and SUSARs) are currently included in the protocol, listed in Section 9.1.2.

- Adverse Reaction: all untoward and unintended responses to an investigational medicinal product related to any dose administered
- Serious Adverse Reaction: an adverse reaction that results in death, is life-threatening, requires hospitalisation or prolongation of existing hospitalisation, results in persistent or significant disability or incapacity, or is a congenital anomaly or birth defect (see Section 9.1.2 for further details pertaining to seriousness criteria)
- Suspected Unexpected Serious Adverse Reaction: a serious adverse reaction, the nature or severity of which is not consistent with the applicable product information (eg, the Investigator's Brochure).

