9.3 Procedures for Reporting a Serious Adverse Event

Any SAE occurring during the study period (beginning with informed consent) until the Follow-up Visit (Visit 8) or 30 days after the last dose of study intervention if the Follow-up Visit is not done must be immediately reported but no later than 24 hours after learning of an SAE.

SAEs must be reported to the sponsor (or agent of the sponsor) as listed on the Study Contacts Page and recorded on the SAE form. All participants with an SAE must be followed up and the outcomes reported. The investigator must supply the sponsor and the IRB/IEC with any additional requested information (eg, autopsy reports and discharge summaries).

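### Serious-event criterion (d) in Protocol 9.1.2 asks for persistent disability only, while Protocol 9.1.6 also counts significant disability and points back to 9.1.2 for the criteria

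*Protocol*

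**What the plan says.** Protocol 9.1.2 lists the outcomes that make an adverse event serious. Criterion (d) is "d. Results in persistent disability/incapacity". A note beneath it begins "The term disability means a substantial disruption" and sets aside events of minor medical importance, such as uncomplicated headache or nausea. Criterion (f) leaves other important medical events to medical or scientific judgement and adds that they should ordinarily be treated as serious.

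Protocol 9.1.6 opens with "For the purposes of expedited reporting within the EU, the sponsor will follow the applicable definitions for ARs, SARs, and SUSARs". Its definition of a serious adverse reaction covers an event that "results in persistent or significant disability or incapacity". The same section states that "seriousness criteria for AEs/ARs (as would apply to SARs and SUSARs) are currently included in the protocol, listed in Section 9.1.2".

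Two other sections give the list its force. Protocol 9.1.3 says an event is serious "when it meets at least one of the predefined outcomes as described in the definition of an SAE", and that a severe rating does not make it so. Protocol 9.3 says an SAE "must be immediately reported but no later than 24 hours after learning of an SAE". SAP 11.1 then defines a treatment-emergent serious adverse event (TESAE) as a treatment-emergent event that also meets an SAE criterion, and tabulates these by arm.

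**The concern.** Section 9.1.6 presents 9.1.2 as the source of the seriousness criteria, so the two should agree. They do not: 9.1.2(d) has no limb for significant disability. The sections also have different users. The sponsor applies 9.1.6 for EU expedited reporting, whereas the site applies 9.1.2 when deciding whether the 24-hour duty has begun. The narrower wording therefore sits at the first step, and the sponsor can apply the wider one only to events it has learned of.

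At stake are the serious classification of an event of this kind, the speed with which the sponsor hears of it, and its place in the TESAE tables. Two sites could classify the same event differently while both follow the protocol.

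**Working it through.** No arithmetic applies. The check is a comparison of the current wording, followed by one test event taken through the criteria.

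**The two wordings**

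| | Protocol 9.1.2(d) | Protocol 9.1.6, serious adverse reaction |
|---|---|---|
| Qualifier | *persistent* | *persistent* or *significant* |
| Main user | Investigator | Sponsor, for EU expedited reporting |
| Consequence | 24-hour report to the sponsor (9.3); TESAE tables (SAP 11.1) | Basis of the serious and suspected unexpected serious reaction definitions |

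**Does the note under (d) close the gap?** No. The note defines disability by degree, as a substantial disruption of normal life functions. *Persistent* stays in the criterion as a separate condition on duration, so (d) needs a disruption that is both substantial and persistent. Section 9.1.6 accepts either persistence or significance.

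**A test event.** Take a disability that the investigator considers drug related, that substantially disrupts normal life and that resolves without hospital admission or risk of death.

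1. Criteria (a), (b), (c) and (e), covering death, threat to life, hospitalisation and congenital anomaly: not met, by construction.
2. Criterion (d): the degree is met but the duration is not, so (d) fails.
3. A severe intensity rating does not help, because 9.1.3 separates severity from seriousness.
4. Criterion (f): available, but through judgement. One limb concerns events that may jeopardise the participant, which could fit. The other concerns intervention to prevent one of the listed outcomes, and so brings back the *persistent* wording of (d).
5. Section 9.1.6: the event is a reaction with significant disability, so it is serious outright.

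The same event is thus serious by definition in one section and serious only by judgement in the other. The direct conflict is confined to events considered related to study drug, since 9.1.6 defines reactions. For unrelated events, 9.1.2(d) is the only wording on disability.

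**What is not lost.** Protocol 9.1.1 requires every adverse event to be recorded in the eCRF, and Protocol 6.5.1 requires severity, causality and seriousness to be assessed for each. The event stays in the database whichever way it is classified.

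**The case against.** The strongest reply is that the other criteria leave little in the gap. Criterion (c) covers hospitalisation and resolves doubt towards serious. Criterion (b) covers threat to life. Criterion (f) leans towards seriousness, and the examples given for it (convulsions or blood dyscrasias without admission) are acute events that need not last. The note under (d) speaks only of degree, so some investigators may already read the criterion that way. Events of special interest have their own immediate or 24-hour reporting route whether or not they are serious (Protocol 6.5.2 and 9.5).

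Most of this stands, and it limits the consequence. It does not remove the mismatch: (f) works through discretion where 9.1.6 does not, and *persistent* remains in (d).

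A reader might also infer more than the documents support:

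- *That each event missed under (d) is a missed expedited regulatory report.* The site's report to the sponsor is a different step. A suspected unexpected serious adverse reaction must also be related and inconsistent with the product information.
- *That DSMB oversight is impaired.* Protocol 3.2 has the board review unblinded safety data and summary reports, which are not confined to SAEs.
- *That an arm's SAE count shifts by some percentage.* The documents give no expected SAE rate and no ground for supposing that an event falls in the gap. Any such figure would rest on two assumptions.
- *That the SAE form repeats the omission, or that past severe events need re-screening.* The form is not in the documents. Severity is also the wrong filter for seriousness under 9.1.3.

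**Conclusion.** The inconsistency is real and lies in the current text. Criterion 9.1.2(d) is narrower than the serious-reaction definition in 9.1.6, although 9.1.6 presents 9.1.2 as the governing list. The residual gap is a disability that is substantial, does not persist, is not life threatening, is not hospitalised and is not taken up under (f). For such an event, 24-hour reporting and inclusion in the TESAE tables depend on site judgement.

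The size is small. Few events are likely to meet all those conditions in a 12-week treatment period, though the documents do not allow a count. Efficacy analyses are unaffected. The conclusion rests on the wording alone and on the assumption that sites apply 9.1.2 as written. It is worth correcting because it concerns a safety-reporting trigger and the correction is nearly free.

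**What to change.** Add *or significant* to criterion 9.1.2(d) so that it matches 9.1.6. This is the natural direction for the change, because 9.1.6 presents its wording as following the applicable EU definitions. Leave the note on minor events in place: it excludes by degree, so routine headache or nausea would not become serious through the added words. Check the disability wording on the SAE form and change it only if it differs.

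The cost is two words in the protocol, one check of the form and notice to sites through the usual amendment route. The TESAE definition in SAP 11.1 needs no edit, because it takes its criteria from the SAE definition.
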